We will conduct the proposed research for the study in two phases. Phase I consists of: (a) the continued development of our current *Invite Only VR* prototype into a polished videogame intervention using input from 4 focus groups of 5 adolescents each (n = 20), aged 12-17 and the extant literature. These focus groups will inform the development of the VR videogame intervention, *Invite Only VR*, for e-cigarette prevention among teens (Specific Aim #1). In Phase II, we will conduct a randomized controlled trial with 300 teens ages 11-15 comparing the *Invite Only VR* intervention vs. an attention/control non-health-related VR videogame, collecting assessment data at baseline, post-gameplay, three months and six months to determine: 1) the preliminary impact of the intervention on knowledge, intentions, perceptions, attitudes, social norms, self-efficacy and behaviors related to initiation of e-cigarette use and e-cigarette use cessation, 2) the intervention's acceptability and feasibility by collecting quantitative and qualitative data on teens' satisfaction and gameplay experience of the intervention, and 3) preliminary evidence of the impact of *Invite Only VR* on players' perception and experience of social pressure and social norm development.

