**Conduct focus groups to gather data to inform refinement of the current videogame prototype, *Invite Only VR*.**

We will conduct 4 focus groups (5 adolescents each) to collect feedback on the game content, art, narrative, and characters, and gameplay mechanics. We will use visual tools (e.g., storyboards, pictures) to facilitate the discussions. We will conduct the focus groups according to standard dual-facilitator procedures. We anticipate that 4 focus groups will be adequate to achieve thematic saturation. The focus groups will be conducted such that ideas and themes from one discussion inform discussion topics and prompts used in the next focus group. Participants will be compensated with a gift card for \$25. Audio recordings of each session will be transcribed, reviewed and discussed by the research team to refine the videogame intervention. As a part of the game development, with parental permission we will invite selected students to the Yale recording studio on campus to provide voices for the videogame characters.

**Conduct randomized controlled trial:** We will enroll 300 adolescents to test *Invite Only VR* using a pre/post design to evaluate the preliminary efficacy of the videogame prototype, *Invite Only VR*. Participants will be randomly assigned to play either Invite Only VR (n=115), or receive standard care as usual (n=115). Participants will accumulate between 1.5-2 hours of game play over 2 sessions (approximately one week, meeting twice). Participants will play the *Invite Only VR* game on a VR headset for 45 mins to 1 hour, one to two times per week for 2 weeks (to accumulate up to 1.5 - 2 hours of gameplay). This total duration and number of sessions is consistent with those found in effective smoking prevention interventions among adolescents and with the amount of time adolescents play videogames. Participants will have a 10 min break in the middle of each session and will be instructed that they may take additional breaks as needed.

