Statistical procedures and models for analyzing data have been selected according to the research hypotheses being investigated and the types of data available. In general, we will use two-tailed tests and p-values smaller than 0.05 will be considered to indicate statistical significance. When necessary, however, we will use appropriate adjustment of the level of significance (alpha) to account for multiple statistical tests. All statistical analyses will be conducted on an intention-to-treat sample using either SPSS/SAS statistical packages. Baseline characteristics will be analyzed using descriptive statistics.

We will evaluate the efficacy of Invite Only VR at reducing initiation of e-cigarette use (primary outcome). We will test the hypothesis that individuals who play Invite Only VR will be less likely to report the initiation of e-cigarette use in comparison to the control condition. We will conduct a longitudinal analysis using a linear mixed models approach to compare participants in the intervention group to participants in the control group on e-cigarette use from baseline across all follow-up assessments. An advantage of mixed models is that participants with missing data need not be excluded as all available data are used in estimating parameters. We will also use logistic regression models to determine if any relevant baseline variables are associated with rates of initiation of e-cigarette use (constructed as a binary outcome (Yes/No). We plan to evaluate the prognostic significance of a small set of predictor variables (e.g., knowledge, intentions, perceptions, attitudes, social norms, and self efficacy) and use them as covariates in the primary analysis.

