### SECTION III: RECRUITMENT/CONSENT AND ASSENT PROCEDURES

1. **Targeted Enrollment: Give the number of subjects: 300 for sub-study 1; 400 for sub-study #2**

- a. Targeted for enrollment at Yale for this protocol: 300; 400  
b. If this is a multi-site study, give the total number of subjects targeted across all sites: n/a

2. **Indicate recruitment methods below.** Attach copies of any recruitment materials that will be used.

- |                                                          |                                                              |                                             |
|----------------------------------------------------------|--------------------------------------------------------------|---------------------------------------------|
|  Flyers               |  Internet/web postings               |  Radio              |
|  Posters              |  Mass email solicitation             |  Telephone          |
|  Letter                          |  Departmental/Center website         |  Television         |
|  Medical record review*          |  Departmental/Center research boards |  Newspaper          |
|  Departmental/Center newsletters |  Web-based clinical trial registries |  Clinicaltrials.gov |
|  YCCI Recruitment database       |  Social Media (Twitter/Facebook):    |                                             |
|  Other:                          |                                                              |                                             |

\* Requests for medical records should be made through JDAT as described at <http://medicine.yale.edu/ycci/oncore/availableservices/datarequests/datarequests.aspx>

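### The logistic models of initiation have no safeguard for few events; if 2–10% initiate and about six predictors enter together, Firth's penalised fit is a cheap improvement to this secondary analysis

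*Combined protocol and SAP*

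**What the plan says.** All of this comes from item 13 unless another place is named.

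- **Outcome.** The stated efficacy target is "reducing initiation of e-cigarette use (primary outcome"). For the logistic models, initiation is "constructed as a binary outcome (Yes/No").
- **Models.** "We will also use logistic regression models to determine if any relevant baseline variables are associated with rates of initiation of e-cigarette use". The fitting method is not given.
- **Predictors.** "We plan to evaluate the prognostic significance of a small set of predictor variables (e.g., knowledge, intentions, perceptions, attitudes, social norms, and self efficacy"). These variables are then to serve as covariates in the primary analysis, which is a linear mixed model.
- **Software.** Analyses are run "using either SPSS/SAS statistical packages".
- **Sample size.** Section III, item 1 gives "300 for sub-study 1; 400 for sub-study #2". Section I, item 4 instead gives two arms for the trial: "Participants will be randomly assigned to play either Invite Only VR (n=115), or receive standard care as usual (n=115").

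There is no initiation rate, expected number of events, dropout rate or limit on predictors relative to events, and no plan for a model that fails to converge.

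**The concern.** Logistic regression without further qualification normally means maximum likelihood. When there are few events for each fitted coefficient, maximum likelihood pushes odds ratios away from 1 on average. Some fits also break down because a combination of predictors separates initiators from the rest. Few events are plausible here: participants are aged 11–15, and follow-up ends at six months.

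At stake are the statements about which baseline variables predict initiation. Effects could be reported as larger than they are. If a fit failed, the replacement method would be chosen after the data had been seen.

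**Working it through.** **Nothing to reproduce.** The plan gives no event count, effect size or power figure. The one available sum is 115 + 115 = 230, which does not match 300, so both sizes are used.

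**Inputs.** N = 300 or 230 and six example predictors come from the documents. The initiation rate is an assumption: 2–10% over six months, with 1% and 20% shown as extremes.

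**Events per predictor** = N × rate ÷ 6, if all six share one model:

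| Rate | Events, N=300 | Per predictor | Events, N=230 | Per predictor |
|---|---|---|---|---|
| 1% | 3 | 0.5 | 2.3 | 0.4 |
| 2% | 6 | 1.0 | 4.6 | 0.8 |
| 5% | 15 | 2.5 | 11.5 | 1.9 |
| 10% | 30 | 5.0 | 23 | 3.8 |
| 20% | 60 | 10 | 46 | 7.7 |

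The true counts could be lower. Never-use at baseline is not an entry criterion (Section I, item 8), so some participants may not be at risk of initiating. The statement in item 13 about using all available data concerns the mixed model, not the logistic models.

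**Bias and failed fits, by simulation** (about 800–1,500 simulated trials per setting; effect sizes and correlations are assumptions). The predictors were six normal variables, correlated 0 or 0.4, with a mix of null effects and odds ratios of about 1.5–2 per standard deviation, or all 1.5.

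Inflation of the maximum-likelihood log odds ratio at N = 300:

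- about 13–26% at a 2% rate
- 8–23% at 3%
- 10–15% at 4%
- 6–10% at 6%
- 4–6% at 10%
- 4–5% at 20%

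At N = 230 the range was about 5–26%.

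On the odds-ratio scale, for a true value of 1.5 (log 0.405):

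- 13% inflation: exp(1.13 × 0.405) = 1.58
- 26% inflation: exp(1.26 × 0.405) = 1.67
- 4% inflation: exp(1.04 × 0.405) = 1.52
- 6% inflation: exp(1.06 × 0.405) = 1.54

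Failed maximum-likelihood fits at N = 300:

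- six continuous predictors: about 1–3% at a 2% rate, under 1% at 3%, none at 5% or 10%
- treatment arm added as a seventh term: about 10% at 2%, about 2–3% at 3%, none at 5% or 10%
- two of the six predictors binary with 15% prevalence: 20% at 2%, 7.6% at 3%, 3.9% at 4%, 0.5% at 6%, none at 10%

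**The same data fitted by Firth's method.** Average bias stayed within about −8% to +1% for continuous predictors, and up to +6% in the variant with binary predictors. Failures nearly vanished at N = 300; at N = 230 with arm included they were at most 1.1%. With arm included at N = 300, root mean square error fell from 0.723 to 0.566 at a 2% rate (1 − 0.566/0.723 = 22%) and from 0.266 to 0.249 at 10% (1 − 0.249/0.266 = 6%).

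**One predictor per model, maximum likelihood, N = 300.** There are then 6–30 events per predictor. The mean log odds ratio was 0.95–1.04 times the truth, with at most 0.1% failures.

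**The case against.** Much of the case on the other side stands.

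- **Rarity is assumed.** A reader might infer that the plan itself implies a rare outcome with 1–5 events per predictor. It gives no rate and does not call the outcome rare.
- **Joint entry is inferred.** The plan speaks of models in the plural, and the six scales are examples. Separate models are a fair reading, and under them the problem almost disappears. Joint entry is also a fair reading, because the variables are treated as a set and carried forward together. The text does not settle it.
- **Failures depend on the model.** One might attribute a failure rate near 10% to the six scales. Most of it comes from adding treatment arm, which item 13 does not list among the baseline predictors.
- **The gain shrinks quickly.** At a 10% rate the bias is 4–6%, no fits fail, and imprecision matters more than bias.
- **Firth is not free.** Mean predicted risk came out near 2.9% against a true 2.0%, and 0.6–0.7 points too high at a 10% rate. Wald 95% intervals covered about 92.5–94% at one event per predictor. In the variant with binary predictors, the median ratio of upper to lower odds-ratio limit for a continuous predictor was still 6.2 at a 2% rate and 2.7 at 10%.

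Against this, item 13 asks about associations rather than predicted risks, and profile intervals are the remedy for the Wald shortfall. Firth also lowered root mean square error at every rate compared. Since the event count is unknown now, fixing the method beforehand avoids a choice driven by a failed or extreme fit.

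**Conclusion.** The concern holds conditionally, as a minor improvement. The absence of any provision for few events is plain from item 13. The size of the harm rests on three assumptions: a 2–10% initiation rate, about six predictors, and joint entry. It is material at 2–3% and slight at 10%.

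A reader might also infer that biased odds ratios pass into the primary analysis because the same variables are reused there. The documents do not support that. The baseline variables enter the linear mixed model as covariates, but the logistic coefficients do not, and changing the logistic fit leaves the primary analysis as it was.

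**What to change.** In item 13:

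1. State which baseline predictors are used, and whether they enter one model or separate models.
2. State that the cross-sectional logistic models of initiation are fitted by Firth's penalised likelihood with profile penalised-likelihood confidence intervals (the FIRTH option in SAS PROC LOGISTIC), and commit these models to SAS.
3. Limit this to the cross-sectional models. The option does not handle within-person correlation, so it should not be applied to repeated-measures binary models.
4. If predicted risks are reported, correct the intercept first.
5. Reconcile 300 with 115 + 115, and state the number at risk of initiation and the expected number of events, so that the predictor list can be judged against them.

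The cost is a few sentences, one option in software the plan already allows, and the loss of a free choice of SPSS for these models. No new data are needed. The change reduces average bias and failed fits; it does not supply the information that few events leave missing.

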**SECTION II: RESEARCH INVOLVING DRUGS, BIOLOGICS, RADIOTRACERS, PLACEBOS AND DEVICES**

- A. RADIOTRACERS  N/A
- B. DRUGS/BIOLOGICS  N/A
- B. DEVICES

- 1. Are there any investigational devices used or investigational procedures performed at Yale-New Haven Hospital (YNHH) (e.g., in the YNHH Operating Room or YNHH Heart and Vascular Center)?  Yes  No

**If Yes, please be aware of the following requirements:**

A YNHH New Product/Trial Request Form must be completed via EPIC: **Pull down the Tools tab in the EPIC Banner, Click on Lawson, Click on "Add new" under the New Technology Request Summary and fill out the forms requested including the "Initial Request Form," "Clinical Evidence Summary", and attach any other pertinent documents. Then select "save and submit" to submit your request; AND**

Your request must be reviewed and approved **in writing** by the appropriate YNHH committee before patients/subjects may be scheduled to receive the investigational device or investigational procedure.

2. **Background Information:** Provide a description of previous human use, known risks, and any other factors that might influence risks. If this is the first time this device is being used in humans, include relevant data on animal models.

*Write here*

3. **Source:**

- a) Identify the source of the device to be used. *Write here*  
b) Is the device provided free of charge to subjects? Yes No

4. **Investigational device accountability:** State how the PI, or named designee, ensures that an investigational device is used only in accordance with the research protocol approved by the HIC, and maintains control of the investigational device as follows:

- a) Maintains appropriate records, including receipt of shipment, inventory at the site, dispensation or use by each participant, and final disposition and/or the return of the investigational device (or other disposal if applicable): *Write here*  
b) Documents pertinent information assigned to the investigational device (e.g., date, quantity, batch or serial number, expiration date if applicable, and unique code number): *Write here*  
c) Stores the investigational device according to the manufacturer's recommendations with respect to temperature, humidity, lighting, and other environmental considerations: *Write here*  
d) Ensures that the device is stored in a secure area with limited access in accordance with applicable regulatory requirements: *Write here*

Distributes the investigational device to subjects enrolled in the IRB-approved protocol: *Write here*

### SECTION III: RECRUITMENT/CONSENT AND ASSENT PROCEDURES

1. **Targeted Enrollment: Give the number of subjects: 300 for sub-study 1; 400 for sub-study #2**

- a. Targeted for enrollment at Yale for this protocol: 300; 400  
b. If this is a multi-site study, give the total number of subjects targeted across all sites: n/a

2. **Indicate recruitment methods below.** Attach copies of any recruitment materials that will be used.

- |                                                          |                                                              |                                             |
|----------------------------------------------------------|--------------------------------------------------------------|---------------------------------------------|
|  Flyers               |  Internet/web postings               |  Radio              |
|  Posters              |  Mass email solicitation             |  Telephone          |
|  Letter                          |  Departmental/Center website         |  Television         |
|  Medical record review*          |  Departmental/Center research boards |  Newspaper          |
|  Departmental/Center newsletters |  Web-based clinical trial registries |  Clinicaltrials.gov |
|  YCCI Recruitment database       |  Social Media (Twitter/Facebook):    |                                             |
|  Other:                          |                                                              |                                             |

\* Requests for medical records should be made through JDAT as described at <http://medicine.yale.edu/ycci/oncore/availableservices/datarequests/datarequests.aspx>

### 3. Recruitment Procedures:

- a. Describe how potential subjects will be identified. SEE BELOW
- b. Describe how potential subjects are contacted. SEE BELOW
- c. Who is recruiting potential subjects? SEE BELOW

#### For sub-study #1

Participation in this study will be strictly voluntary, confidential and non-discriminatory. Participants will be enrolled while they are on-site at one of the participating programs. The study will be advertised via posters and flyers located and circulated at the two community centers with which we have partnered. Potential participants will meet with the Research Assistant to discuss participation in the study. For the RCT, if the participant is interested, the Research Assistant will discuss the study with their guardian/parent and obtain informed written assent from the participant and written informed consent from their guardian/parent. For the focus groups, the Research Assistant will discuss the study with their guardian/parent and obtain verbal assent from the participant and verbal consent from their guardian/parent. Participants will be provided with an age-appropriate description of the study and told about what they might expect. In describing the study to the participant, the purpose of the study will be described as “finding out how kids can make choices that are healthier for them”. In describing the study to the guardian/parent, we will indicate that the study will focus on promoting healthy behaviors in adolescence and on providing strategies to assist adolescents in making decisions about the many challenges they face; particularly as they relate to avoiding tobacco use. If a participant or their guardian/parent indicates that they do not wish to participate, there will be no further involvement in the study. We will also obtain agreement from the appropriate administrator at the participating program.

In addition to paper forms for parental consent for participation in the randomized controlled study, we will also provide a web-based form for parents to review and electronically sign through Yale Qualtrics.

#### For sub-study #2

Participation in this study will be strictly voluntary, confidential and non-discriminatory. Participants will be enrolled while they are on-site at one of school classrooms in Seattle Schools. For the quasi-experimental study, information sheets will be provided to the adolescents and parents about the study. If a parent does not wish their child to participate, they can call the designated school program staff to opt out. An email will also be provided later to all student’s parents about the study as a second means of ensuring the letter reaches the parents. If a participant or their guardian/parent indicates that they do not wish to participate, there will be no further involvement in the study.

The PI from the research team ([name]) will Zoom in to each classroom to discuss the study with students over video and consent them into the research. In addition to the opportunity to contact the PI with questions during recruitment, students will have the time to ask questions regarding the study and will be provided with a phone number to speak with [name] directly if they desire. Parents will also be provided a phone number in the verbal consent sheet so that they may contact her directly with questions or more information.

### 4. Assessment of Current Health Provider Relationship for HIPAA Consideration:

Does the Investigator or any member of the research team have a direct existing clinical relationship with any potential subject?

- Yes, all subjects
- Yes, some of the subjects
- No

If yes, describe the nature of this relationship. *Write here*

**5. Request for waiver of HIPAA authorization:** (When requesting a waiver of HIPAA Authorization for either the entire study, or for recruitment purposes only. Note: if you are collecting PHI as part of a phone or email screen, you must request a HIPAA waiver for recruitment purposes.)

**Choose one:**

- For entire study
- For recruitment/screening purposes only
- For inclusion of non-English speaking subject if short form is being used and there is no translated HIPAA research authorization form available on the University's HIPAA website at [hipaa.yale.edu](http://hipaa.yale.edu).

- i. Describe why it would be impracticable to obtain the subject's authorization for use/disclosure of this data: *Write here*
- ii. If requesting a waiver of **signed** authorization, describe why it would be impracticable to obtain the subject's signed authorization for use/disclosure of this data: *Write here*

**The investigator assures that the protected health information for which a Waiver of Authorization has been requested will not be reused or disclosed to any person or entity other than those listed in this application, except as required by law, for authorized oversight of this research study, or as specifically approved for use in another study by an IRB.**

*Researchers are reminded that unauthorized disclosures of PHI to individuals outside of the Yale HIPAA-Covered entity must be accounted for in the "accounting for disclosures log", by subject name, purpose, date, recipients, and a description of information provided. Logs are to be forwarded to the Deputy HIPAA Privacy Officer.*

**6. Process of Consent/Assent:** Describe the setting and conditions under which consent/assent will be obtained, including parental permission or surrogate permission and the steps taken to ensure subjects' independent decision-making.

Sub-study #1

Participation in this study will be strictly voluntary, confidential and non-discriminatory. Participants will be enrolled while they are on-site at one of the participating programs. The study will be advertised via posters and flyers located at the two listed community sites. Potential participants will meet with the Research Assistant to discuss participation in the study. If the participant is interested, the Research Assistant will discuss the study with their guardian/parent. We will provide the adolescents and their parents with an age-appropriate description of the study and told about what they might expect. In describing the study to the participant, the purpose of the study will be described as "finding out how kids can make choices that are healthier for them". In describing the study to the guardian/parent, we will indicate that the study will focus on promoting healthy behaviors in adolescence and on providing strategies to assist adolescents in making decisions about the many challenges they face; particularly as they relate to tobacco use. For the focus

groups we will employ waived signature of consent. Parents who do not wish for their children to participate will contact the project director. For the evaluation, we will obtain informed written assent from the participant and written informed consent from their guardian/parent. For both phases, if a participant or their guardian/parent indicates that they do not wish to participate, there will be no further involvement in the study. We will also obtain agreement from the appropriate administrator at the participating program.

In addition to paper forms for parental consent for participation in the randomized controlled study, we will also provide a web-based form for parents to review and electronically sign through Yale Qualtrics.

